9.3.1.2 Primary Analysis

The primary efficacy analysis will be using the MCP-Mod approach to detect the dose-response relationship from a candidate set of 4 dose-response models (Linear, Emax, Logistic, and Sigmoid Emax). Dose level 2 and Dose level 3 of VX-150 group will be combined into one treatment group in the MCP-Mod procedure. Total dose on Day 1 for each treatment group will be used in the MCP-Mod procedure as shown in Table 9-1.

Table 9-1 VX-150 Doses by Treatment in Primary Analysis

Treatment	Dose Level	Dose	Total Dose on Day 1	Analysis Treatment Group	
VX-150	First dose 1500 mg, then 750 mg q12h		2250 mg	VX-150 Dose Level 1	
	2	1000 mg qd	1000	VX-150 Dose Level 2/3	
	3 500 mg q12h		1000 mg	VA-130 Dose Level 2/3	
	4	First dose 500 mg, then 250 mg q12h	750 mg	VX-150 Dose Level 4	
	5 (lowest)	250 mg qd	250 mg	VX-150 Dose Level 5	
Placebo			0 mg	Placebo	

MCP-Mod approach will be based on an analysis of covariance (ANCOVA) model. The model will include SPID24 after the first dose as the dependent variable, treatment as a fixed effect, with site, sex, and baseline pain intensity score as covariates. The Least Squares (LS) means (SE) and 95% confidence interval (CI) will be provided for each treatment group. From the MCP-Mod procedure, the 2-sided *P* value will be provided for each dose-response model in the candidate set. If at least one dose-response model in the candidate set is statistically significant, a dose-response model will be selected based on the maximum test statistic criterion. The selected dose-response model will be estimated and presented in a figure.

Pain intensity scores used for the primary analysis will be summarized descriptively including SE by treatment at each scheduled time point and the mean values over time by treatment will be presented in a figure. SPID24 used for the primary analysis will also be summarized descriptively including SE by treatment.

9.3.2 Analysis of Secondary Efficacy Variables

9.3.2.1 Definition of Secondary Efficacy Variables

Time-weighted sum of the pain intensity difference between VX-150 versus placebo as recorded on a NPRS 0 to 48 hours (SPID48) after the first dose: SPID48 will be calculated using the following formula:

 $\begin{array}{l} \bullet \quad SPID48 = 0.5 \times PID_{0.5} + 0.5 \times PID_1 + 0.5 \times PID_{1.5} + 0.5 \times PID_2 + PID_3 + PID_4 + PID_5 \\ + PID_6 + 2 \times PID_8 + 4 \times PID_{12} + 4 \times PID_{16} + 4 \times PID_{20} + 4 \times PID_{24} + 4 \times PID_{28} + 4 \times PID_{32} + 4 \times PID_{36} + 4 \times PID_{40} + 4 \times PID_{44} + 4 \times PID_{48} \end{array}$

Proportions of subjects with at least 30%, 50%, or 70% reduction in NPRS at 24 hours after the first dose of VX-150 versus placebo: A subject with at least 30%, 50%, or 70% reduction in NPRS at 24 hours after the first dose of study drug will be defined as a "responder". The percentage reduction in the NPRS will be calculated as following:

• 100 × (NPRS at baseline –NPRS at 24 hours) / NPRS at baseline

If a subject discontinues the study drug treatment for any reason prior to 24 hours, this subject will not be a "responder" for any of the three criteria. If a subject has missing NPRS at 24 hours without discontinuing the study drug treatment prior to 24 hours, the LOCF principle will be used to impute pain intensity score at 24 hours. The last observed pain intensity score should be from a regularly scheduled measurement including a previous prerescue assessment, but cannot be any actual measurements taken during a previous rescue period.

Time to onset of "confirmed perceptible pain relief" and "meaningful pain relief" after the first dose of VX-150 versus placebo: Time to onset of "perceptible pain relief" is the time elapsed from first dose of VX-150 or placebo until the subject stops the "perceptible pain relief" stopwatch. Time to onset of "meaningful pain relief" is the time elapsed from first dose of VX-150 or placebo until the subject stops the "meaningful pain relief" stopwatch. Time to onset of "confirmed perceptible pain relief" will be defined as the time to onset of perceptible pain relief for those subjects who had meaningful pain relief.

If the subject has not stopped the stopwatch by 6 hours after the first dose, the stopwatch will be stopped and time to onset will be considered censored at 6 hours. If the subject receives rescue medication during the first 6 hours, the stopwatch will be stopped immediately before administration of rescue medication and time to onset will be considered censored at the time of rescue medication plus 4 hours or at 6 hours, whichever happened earlier. If perceptible pain relief is obtained without associated meaningful pain relief, time to onset of "confirmed perceptible pain relief" will also be considered censored at 6 hours.

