11.4 Efficacy

Pain scales: After removal of the popliteal sciatic block, a subject can be randomized once the subject requests the first dose of study drug for pain relief, and the subject's pain is ≥4 on the NPRS and is moderate or severe on the VRS. If a subject does not meet the NPRS and VRS criteria within 9 hours of removal of the popliteal sciatic block, the subject will not be eligible for the study.

Subjects will report their pain on the NPRS at scheduled time points (Table 3-2) through 48 hours after the first dose of study drug. In addition, pain intensity will be recorded on the NPRS scale immediately before each administration of rescue medication.

When NPRS assessments coincide with collection of PK blood samples, the NPRS assessment will be performed first.

Double-stopwatch assessment: At the time of first dose, 2 stopwatches will be started: 1 labeled "perceptible pain relief" and the other labeled "meaningful pain relief." Subjects will stop the "perceptible pain relief" stopwatch when/if they feel any pain relief at all and stop the "meaningful pain relief" stopwatch when/if they feel relief that is "meaningful" to them. If the subject does not stop both stopwatches by 6 hours after the first dose, or receives rescue medication, the stopwatches will be stopped.

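### Rescued subjects are censored for onset up to 4 hours after their stopwatch has stopped, a rule that is neither standard censoring nor a consistent rescue-as-failure rule

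*SAP*

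**What the plan says.** SAP 9.3.2.1 defines each onset time by the subject's own action. For meaningful relief it is the time from first dose "until the subject stops the 'meaningful pain relief' stopwatch", and perceptible relief is defined in the same way. Confirmed perceptible relief is perceptible relief in subjects who also reach meaningful relief.

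The same section then sets three censoring rules:

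- No stop by 6 h: "the stopwatch will be stopped and time to onset will be considered censored at 6 hours".
- Rescue within 6 h: on the watch itself, the SAP says that "the stopwatch will be stopped immediately before administration of rescue medication". It sets the censoring time separately: "time to onset will be considered censored at the time of rescue medication plus 4 hours or at 6 hours, whichever happened earlier".
- Perceptible but not meaningful relief: the confirmed perceptible endpoint "will also be considered censored at 6 hours".

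Protocol 11.4 agrees on the watch ("If the subject does not stop both stopwatches by 6 hours after the first dose, or receives rescue medication, the stopwatches will be stopped") but gives no censoring time. SAP 9.3.2.2 uses these times in Cox models comparing each dose level with placebo, adjusted for site and sex, and in Kaplan-Meier curves. The visible text has no sensitivity analysis with censoring at rescue.

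**The concern.** An onset exists only if the subject stops a running watch. Once the watch is stopped for rescue, the subject cannot have an event, so the last time at which the subject was observed without relief is the rescue time. The SAP nevertheless counts up to 4 further hours as time at risk. The SAP's only stated 4-hour rescue assumption, in 9.3.1.1, concerns pain scores. No reason is given for using 4 hours with a stopwatch.

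The added time goes only to subjects rescued before relief, so an arm with more such rescue carries more of it and shows a lower apparent onset rate. If placebo is that arm, a hazard ratio above 1 could reflect less rescue on VX-150 as well as faster relief, and the SAP does not tell the reader which is meant. Onset is a named secondary endpoint in a study intended to inform Phase 3 dose selection.

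**Working it through.** The documents give no power, event count or hazard ratio for the onset endpoints, so there is no planned figure to reproduce.

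**1. Time credited after the watch stops.** Let R be the rescue time in hours. Censoring under the SAP is at min(R + 4, 6), so the credited time is min(R + 4, 6) − R.

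| R | Standard censoring | SAP rule | Uniform 6-hour rule | Credited time under SAP |
|---|---|---|---|---|
| 0.5 | 0.5 | 4.5 | 6 | 4 |
| 1 | 1 | 5 | 6 | 4 |
| 2 | 2 | 6 | 6 | 4 |
| 3 | 3 | 6 | 6 | 3 |
| 4 | 4 | 6 | 6 | 2 |
| 5 | 5 | 6 | 6 | 1 |

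From R = 2 h onward the SAP rule equals the 6-hour rule. Below 2 h it does not, and the subjects rescued earliest leave the risk set first. Rescue before 2 h is possible: the 90-minute wait is only encouraged, and rescue is available on request at any time (Protocol 9.1, SAP 7.1).

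**2. Conflict within the paragraph.** Take perceptible relief at 0.5 h, rescue at 1 h and no meaningful relief. For confirmed perceptible relief, the rescue sentence censors at 1 + 4 = 5 h and the next sentence at 6 h. No precedence is stated. The two differ whenever R + 4 < 6, that is, for rescue before 2 h.

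**3. Effect on the hazard ratio.** All rates here are assumptions. Onset is exponential with the same hazard in both arms (0.1 to 0.3 per hour, true HR 1.0). Rescue is independent of onset. Relief before rescue counts as an event. The Cox model contains treatment only. Rescue percentages are by 6 h in the absence of relief, placebo v active. Entries are large-sample HRs (200,000 per arm), as ranges over the onset hazards.

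| Rescue | Starts | Censor at rescue | SAP rule | 6-hour rule |
|---|---|---|---|---|
| 50% v 50% | 1.5 h | 1.00 | 1.00 | 1.00 |
| 60% v 40% | 1.5 h | 1.00–1.01 | 1.10–1.12 | 1.10–1.12 |
| 70% v 40% | 1.5 h | 1.00 | 1.16–1.20 | 1.16–1.20 |
| 80% v 30% | 1.5 h | 1.00–1.01 | 1.27–1.37 | 1.28–1.38 |
| 50% v 50% | 0 h | 0.99–1.00 | 0.99–1.00 | 0.99–1.00 |
| 60% v 40% | 0 h | 0.99–1.00 | 1.17–1.18 | 1.19–1.20 |
| 70% v 40% | 0 h | 1.00–1.01 | 1.31–1.33 | 1.33–1.35 |
| 80% v 30% | 0 h | 1.00–1.01 | 1.60–1.63 | 1.66–1.70 |

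Separate runs with 50% onset by 6 h and rescue from 1.5 h, at 60% v 30%, 70% v 40% and 80% v 40%, gave HRs of 1.17, 1.19 and 1.30 under the SAP rule. With 44 per arm, two-sided rejection at nominal 5% was 7.5%, 7.1% and 10.7%, against 4.5% to 6.2% when censoring at rescue. For 80% v 40% with rescue from 0 h, the HR is about 1.5.

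As one worked case, take hazard 0.2 per hour and rescue 70% v 40% from 1.5 h. The credited time averages 1.09 h per placebo subject and 0.55 h per active subject, or 29% v 15% of analysed person-time. The HR is 1.17, and rejection is 8.5% against 4.8% when censoring at rescue. With rescue from 0 h, the shares are 41% v 22%, the HR is 1.33 and rejection is 13.7%.

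**4. When rescue and onset are related.** With a frailty shared by rescue and onset and no true effect, censoring at rescue gives HRs of about 0.87 to 0.99. In one set of such runs the SAP rule gave 1.13 to 1.21.

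**The case against.** The strongest reply is that this is a choice of estimand, not an error. Keeping a rescued subject as a non-event is how one analyses rescue as lack of relief from study drug. From 2 h onward the SAP rule does exactly that, and subjects are encouraged to wait 90 minutes. With rescue from 1.5 h, the SAP and 6-hour HRs differ by only about 0.002 to 0.003 in runs reported to three decimals (for example 1.194 v 1.196). With rescue from 0 h the gap is about 0.02 to 0.07, and the SAP value is the one closer to 1.

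Most of this stands. A reader might infer that the whole shift in HR is bias in favour of VX-150. The documents do not support that: they give no rescue rates by arm and state no target for these endpoints, and a legitimate rescue-as-failure analysis shows nearly the same shift. Nor is it assured that all five comparisons are affected. Equal rescue gives no shift, and SAP 9.3.2.2 drops any dose level with fewer than 5 events. That the 4 hours was borrowed from the pain-score rule is plausible but not stated.

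It is also fair that censoring at rescue is not neutral, since subjects take rescue because they lack relief. And a drug that lowers rescue sharply with no effect on onset is an extreme null case.

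The reply does not rescue the rule as written. The SAP does not say that rescue counts as failure, the rule departs from that reading for rescue before 2 h, and the conflict for confirmed perceptible relief remains.

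**Conclusion.** The point holds as a defect of definition. Rescued subjects are carried for up to 4 h in which no onset can be recorded, under a rule that matches neither standard censoring nor a consistent rescue-as-failure analysis. For confirmed perceptible relief with rescue before 2 h, the paragraph gives two censoring times.

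The size depends wholly on assumed rescue rates. With more rescue on placebo (60% v 30%, 70% v 40%, 80% v 40%) and no true onset effect, the HR is about 1.1 to 1.3 with rescue from 1.5 h and up to about 1.5 with rescue from 0 h. The wider contrast of 80% v 30% reaches 1.37 and 1.63. With equal rescue and no true effect there is no shift. With equal rescue and a true HR of 1.5, the HR shrinks slightly, to about 1.45.

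This is a bias only if the target is onset in the absence of rescue. Otherwise the HR is a blend of onset and rescue avoidance that the SAP does not name. The endpoints are secondary and carry no multiplicity adjustment, and the primary MCP-Mod analysis of SPID24 is untouched.

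**What to change.** In SAP 9.3.2.1:

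1. Replace the rescue clause quoted above so that a subject rescued before onset is censored at the time of the rescue dose.
2. State one censoring time for subjects with perceptible but not meaningful relief who are rescued. Change 1 makes this necessary: with censoring at R, the 6-hour sentence would conflict for every rescue before 6 h, not only before 2 h.
3. Add a labelled analysis that keeps all rescued subjects as non-events to 6 h.
4. Say what each analysis estimates: onset in the absence of rescue for the first, relief without rescue within 6 h for the second.

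The cost is SAP wording and one further set of model runs on data already collected. The downside is that censoring at rescue is likely informative and can pull the HR below 1 when there is no effect, so the two results should be read together. The onset hazard ratios may also look less favourable than under the present rule.

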9.3.2.2 Secondary Analyses

Time-weighted sum of the pain intensity difference between VX-150 versus placebo as recorded on a NPRS 0 to 48 hours (SPID48) after the first dose: Same imputation strategies as described for SPID24 in Section 9.3.1.1 will be applied to SPID48.

[figure not shown]
Proportions of subjects with at least 30%, 50%, or 70% reduction in NPRS at 24 hours after the first dose of VX-150 versus placebo: Analysis of responder rates between each individual dose level of VX-150 and placebo will be conducted using Cochran-Mantel-Haenszel test, stratified by site and sex.

Time to onset of "confirmed perceptible pain relief" and "meaningful pain relief" after the first dose of VX-150 versus placebo: Time to onset of "confirmed perceptible pain relief" will be analyzed using Cox regression model. The model will include treatment, site and sex as covariates. Pairwise comparison between each individual dose level of VX-150 and placebo will be conducted under the model.

Note: If placebo group has fewer than 5 subjects experience "confirmed perceptible pain relief", the Cox regression will not be performed. If any dose level of VX-150 group has fewer than 5 subjects experience "confirmed perceptible pain relief", the particular dose level group will not be included in the Cox regression model.

Additionally, the Kaplan-Meier method will be used to produce graphical presentation of the survival curves by treatment group.

Time to onset of "meaningful pain relief" and time to onset of "perceptible pain relief" will be analyzed in the same way as described for time to onset of "confirmed perceptible pain relief".

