8.1 Inclusion Criteria

Before surgery:

- 1. Subject will sign and date an informed consent form (ICF)
- 2. Willing and able to comply with scheduled visits, treatment plan, study restrictions, laboratory tests, contraceptive guidelines, and other study procedures
- 3. Body mass index (BMI) of 18.0 to 38.0 kg/m², inclusive

- 4. Subjects (male and female) will be between the ages of 18 and 65 years, inclusive
- 5. Be scheduled to undergo a primary unilateral first metatarsal bunionectomy repair, without collateral procedures, under regional anesthesia (Mayo and popliteal sciatic block) not to include base wedge procedure

After surgery:

- 6. Subject reported pain of ≥4 on the NPRS and moderate or severe pain on the Verbal Categorical Rating Scale (VRS) within 9 hours after removal of the popliteal sciatic block on Day 1.
- 7. Subject is lucid and able to follow commands.
- 8. All analgesic guidelines (Section 9.4.1) were followed during and after the bunion ectomy.

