12.3.3.2 Analysis of Secondary Efficacy Variables

- Time-weighted sum of the pain intensity difference between VX-150 versus placebo as recorded on a NPRS 0 to 48 hours (SPID48) after the first dose: analysis of this variable will be similar to the primary analysis.
- Proportions of subjects with at least 30%, 50%, or 70% reduction in NPRS at 24 hours after the first dose of VX-150 versus placebo: This variable will be analyzed using the Cochran-Mantel-Haenszel test, stratified by site and sex.
- Time to onset of "confirmed perceptible pain relief" after the first dose of VX-150 versus placebo: This variable will be analyzed using Cox regression model. The model will include a covariate for treatment and adjustment for site and sex. Additionally, the Kaplan-Meier method will be used to produce graphical presentation of the survival curves by treatment group and to estimate survival rates by treatment group.
- Time to onset of "meaningful pain relief" after the first dose of VX-150 versus placebo: The analysis of this variable will be similar to the analyses of time to onset of "perceptible pain relief."

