7.2 Sample Size and Power

The sample size calculation is based on the primary analysis of the primary efficacy endpoint. The primary efficacy endpoint is the time-weighted sum of the pain intensity difference 0 to 24 hours after the first dose (SPID24). The primary analysis of this endpoint is to detect if there is a significant dose-response relationship across VX-150 dose groups and placebo using the MCP-Mod (multiple comparison procedures with modeling techniques). Under MCP-Mod, a pre-specified candidate set of 4 dose-response models (Linear, Emax, Logistic, and Sigmoid Emax) is proposed.

Assuming the maximum effect size compared to placebo is 0.7, 40 evaluable subjects in the placebo, VX-150 Dose Level 1 (highest), 2, 3, and 4 groups, and 20 evaluable subjects in VX-150 Dose Level 5 (lowest) group would provide approximately at least 88% power to detect a dose-response relationship from the candidate set with a 5% level of significance. In addition, 40 evaluable subjects per treatment group can provide at least 85% power to detect an effect size of 0.7 compared to placebo. In order to allow for withdrawal of up to 10% of randomized subjects, the study will enroll and randomize approximately 242 subjects in total.

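### The Cox models for onset of pain relief leave out baseline NPRS, a covariate that is already collected, costs almost nothing to add and may gain a few points of power

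*SAP*

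**What the plan says.** **Onset of relief.** SAP 9.3.2.2 analyses time to confirmed perceptible relief by Cox regression: "The model will include treatment, site and sex as covariates". It compares each VX-150 dose with placebo within that model, and handles meaningful relief and perceptible relief in the same way, which makes three onset analyses. Protocol 12.3.3.2 agrees on the terms: "The model will include a covariate for treatment and adjustment for site and sex".

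**Responders (30%, 50%, 70%).** SAP 9.3.2.2 says the comparison of each dose with placebo "will be conducted using Cochran-Mantel-Haenszel test, stratified by site and sex". SAP 9.3.2.1 defines the percentage reduction as "100 × (NPRS at baseline –NPRS at 24 hours) / NPRS at baseline".

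**Primary analysis.** The SPID24 ANCOVA (SAP 9.3.1.2) has "treatment as a fixed effect, with site, sex, and baseline pain intensity score as covariates". Protocol 12.3.3.2 says SPID48 is analysed similarly.

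**Availability of baseline.** Protocol 8.1 requires: "Subject reported pain of ≥4 on the NPRS and moderate or severe pain on the Verbal Categorical Rating Scale". SAP 9.1 defines baseline NPRS as the latest Day 1 score before the first dose.

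Neither document explains why baseline NPRS enters the SPID analyses and not the onset models.

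**The concern.** How soon a subject reports relief may well depend on how much pain the subject starts with. When a prognostic covariate is left out of a Cox model, the estimated treatment hazard ratio moves toward 1 and the test loses power. A chance difference in starting pain between two small arms also goes uncorrected. The onset comparisons are dose by dose against placebo, in a trial meant to inform dose selection for Phase 3 (Protocol 5.2), so clearer estimates have practical value. The covariate needs no new data.

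**Working it through.** **1. The plan's own power figure.** SAP 7.2 claims at least 85% power with 40 evaluable subjects per group and an effect size of 0.7, having set the dose-response test "with a 5% level of significance". Two-sided normal approximation: power = Φ(0.7 × √(40/2) − 1.960) = Φ(3.130 − 1.960) = Φ(1.170) = 87.9%; the noncentral t gives 87.1%. The claim is met, but it concerns SPID24. No power is stated for the onset or responder analyses.

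**2. Inputs for the onset models.**
- From the documents: arms of 44, with 22 for Dose Level 5 (SAP Table 7-1); follow-up to 6 hours (SAP 9.3.2.1); model terms as quoted.
- Assumed, because the documents give no figure: treatment hazard ratio (HR) 2.2, placebo onset hazard 0.12/h, rescue censoring 0.08/h, 4 sites, 15% male, two-sided 5% test, and the HR per NPRS point of baseline.

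**3. Six-arm Cox model, 1,500 runs per setting.** Power without → with baseline NPRS:

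| HR per NPRS point | 44 v 44 | Gain | 22 v 44 | Gain |
|---|---|---|---|---|
| 1.00 | 77.1 → 76.7% | −0.4 | 62.3 → 63.1% | +0.8 |
| 0.90 | 75.7 → 76.8% | +1.1 | 59.1 → 60.5% | +1.4 |
| 0.82 | 73.9 → 77.1% | +3.2 | 58.4 → 62.5% | +4.1 |
| 0.74 | 69.7 → 75.1% | +5.4 | 54.4 → 61.3% | +6.9 |

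The Monte Carlo standard error of one power figure near 75% is √(0.75 × 0.25 / 1500) = 1.1 points. At 0.74 the estimated treatment HR is 2.26 with baseline and 2.11 without. Type I error with baseline in the model was 4.5 to 5.3%.

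**4. Other settings, 44 v 44.**
- Two arms, no site or sex terms, 600 runs (standard error about 1.8 points): 74.8 → 74.5% at 1.00, 76.0 → 77.3% at 0.90, 74.5 → 79.5% at 0.82, 70.8 → 77.5% at 0.74, 61.8 → 75.5% at 0.67.
- Two arms with site and sex terms, 3 sites, no rescue, 1,500 runs, strength set per SD of baseline: 84.9 → 84.5% at 1.0, 82.6 → 82.6% at 0.85, 80.5 → 83.2% at 0.75, 74.5 → 82.9% at 0.6, 67.9 → 80.7% at 0.5.

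With an assumed SD of 1.7, 0.74 per point is 0.74^1.7 = 0.60 per SD. The comparable gains at that strength are therefore +5.4, +6.7 and +8.4 points. The last comes from the simpler setting without rescue censoring.

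**5. Few events.** With placebo hazard 0.03/h (about 58 events over six arms), power was 32.7 → 32.9% when baseline was not prognostic and 31.8 → 33.3% at 0.82 per point. The extra term cost nothing measurable.

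**6. Responders: which change produces the gain?** 24-hour NPRS simulated with an assumed slope on baseline; 30% criterion, 44 v 44, 5 sites assumed, 2,500 runs:

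| Slope | CMH | Logistic, no baseline | Logistic + baseline | From change of test | From baseline |
|---|---|---|---|---|---|
| 0.3 | 57.3% | 62.5% | 64.6% | +5.2 | +2.1 |
| 0.5 | 62.5% | 67.3% | 67.6% | +4.8 | +0.3 |
| 0.7 | 62.4% | 66.2% | 66.4% | +3.8 | +0.2 |

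A separate two-arm run over slopes 0 to 1.0 and all three criteria found that adding a baseline stratum (below 7 v 7 or more) to the CMH changes power by −3.2 to +0.4 points. Adding baseline to a logistic model changed it by −0.2 to +6.4. The largest value came at slope 0 with the 30% criterion (49.4 → 55.8%). At slopes 0.3 to 0.8 baseline added at most 2.7 points.

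**The case against.** **The gain is assumed.** This stands. The documents give no prognostic strength for onset, and the stronger settings are demanding: 0.74 per point means a hazard ratio of 1/0.74^6 ≈ 6 between NPRS 4 and 10, and 0.67 per point means about 11. At weak strength the gain is about 1 point. The simulations also did not reproduce the SAP's censoring at rescue plus 4 hours or 6 hours, whichever is earlier.

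**The ANCOVA sets no precedent.** A reader might infer that the plan accepts baseline NPRS as prognostic for onset because the primary model includes it. It does not follow: SPID24 is computed from baseline minus later scores, so adjustment is natural there, whereas stopwatch times are not computed from baseline. The ANCOVA shows only that the covariate is available and already handled.

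**Few events.** The SAP drops a dose from the Cox model when it has fewer than 5 events, so an extra term might look risky. The low-event run showed no measurable cost.

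**The responder test.** A reader might extend the point to the responder analysis, arguing that on an integer scale the 30% criterion demands a 50% drop from 4 but only 30% from 10. The full sequence for baselines 4 to 10 is 50, 40, 33, 43, 37.5, 33, 30%: a sawtooth that a linear term would not capture. For the 50% criterion it is 50, 60, 50, 57, 50, 56, 50%, with no trend. The endpoint already divides by baseline. At intermediate slopes most of the logistic model's advantage comes from pooling sparse site-by-sex cells, which is a separate question. Replacing the planned test is a trade-off, not a free gain.

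**Conclusion.** The point holds for the three onset Cox models as a low-cost improvement, not as an error. Under assumed baseline HRs of 1.0 to 0.74 per NPRS point, the six-arm model gains about 0 to 7 points of power. One simpler two-arm setting of similar strength gives about 8, and about 13 to 14 appears only when baseline is very strongly prognostic. With non-prognostic baseline the change was within simulation error (−0.4 to +0.8 points).

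Two stronger readings are not supported. The first is that the onset and responder analyses both give up power for nothing: the loss depends on an unknown prognostic strength, and the responder gain comes mainly from changing the test at slopes 0.3 to 0.8 (the exceptions lie at the extreme slopes). The second is that the planned analyses are invalid: they adjust for both stratification factors, and these are secondary analyses with no stated power and no multiplicity control (SAP 9.1). Adjusted and unadjusted hazard ratios are also slightly different quantities, so the shift from 2.26 to 2.11 should not be read as bias in a faulty test.

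**What to change.** Before database lock, amend the Cox model sentence in SAP 9.3.2.2 so that the covariates are treatment, site, sex and baseline NPRS as a continuous term, using the SAP 9.1 definition of baseline. Apply it to confirmed perceptible, meaningful and perceptible relief. Align Protocol 12.3.3.2, or record the added covariate as a change from the protocol; a protocol modification needs investigator and sponsor approval (Protocol 13.2.3).

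Keep the site-by-sex CMH test as the responder analysis. A logistic model with treatment, site, sex and baseline NPRS may be listed as supportive. If it is, state in advance the minimum number of responders needed to fit it, because the 70% criterion may be sparse.

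Cost: one degree of freedom per Cox model and the wording changes. No new data or subjects are needed.
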